**Note: If an event is reported at multiple follow-up visits, the earliest available date will be used for analysis.**

## 8.2 Analysis methods

If not otherwise stated, the analyses will be performed on the full analysis set.

### 8.2.1 Patients' characteristics (table 1)

The following summary statistics will be reported for quantitative variables:

- mean (sd)
- median (IQR)
- range (min – max)

The descriptive analysis will allow completion of the following table

**Table 1 – Baseline Demographic and Clinical Characteristics (Full Analysis Set)**

Patients' characteristics	CXR (n=XXX)	LDCT (n=YYY)	LUS (n=ZZZ)
Age* (years)			
>80 yr			
Gender, n (%)			
Male			
Female			
BMI* (kg/m^2)			
Underweight (< 18.5)			
Normal (≥ 18.5 & < 25)			
Overweight (≥ 25 & < 30)			
Obese (≥ 30)			
Smoking status			
Never smoked			
(Past or current) smoker			
Place of living			
Living at home			
Living in nursing home / supportive residence			
Activities of daily living before admission (Katz)			
Independent (ADL<5)			
Partially dependent (ADL=5)			
Dependent (ADL=6)			
Instrumental activities of daily living before admission (Lawton)			
Independent (IADL<5)			
Partially dependent (IADL≥5 et <7)			
Dependent (IADL≥7)			
Frailty (Rockwood scale)			
Robust (=0)			

Pre-frail (=1 ou 2)  
Frail (>=3)  
NRS score (malnutrition)  
No risk (< 3)  
At risk (>= 3)  
Cognition (MMSE)  
Normal (>= 24)  
Mild impairment score (>= 18 & < 24)  
Severe impairment (< 18)  
Hospitalisation during the past 6 months, n/N (%)  
Influenza vaccination within the past year, n/N (%)  
Pneumococcal vaccination in the past 5 years, n/N (%)  
Vaccination against SARS CoV-2, n/N (%)

### **Comorbidities**

Chronic cardiac disease, n (%)  
COPD, n (%)  
Kidney disease, n (%)  
Liver disease, n (%)  
Diabetes, n (%)  
Stroke, n (%)  
Active neoplasia, n (%)  
Cognitive disorders, n (%)  
Swallowing disorders, n (%)  
Immunosuppression, n (%)  
Number of comorbidities, n (%)  
0  
1  
2 or more  
Polypharmacy ( $\geq 5$  medications taken daily)  
No  
Yes  
Charlson comorbidity index\*

### **Clinical characteristics of pneumonia**

Type of pneumonia  
Community-acquired pneumonia  
Nursing-home pneumonia  
Temperature  $\geq 38.0$  °C  
Cough  
Dyspnea  
Sputum production  
Chest pain  
Crackles  
Pleural effusion  
Decrease in respiratory sounds  
Peripheral oxygen saturation <90% on room air  
Respiratory rate

Anorexia  
Asthenia  
Delirium  
Fall  
Rhinorrhea  
Maylgia

#### **Severity scores**

CURB-65\*

Low (<=1)

Moderate (=2)

High (>=3)

Fine score

Classe I (<50)

Class II (>= 50 & <= 70)

Class III (>= 71 & <= 90)

Class IV (>= 91 & <= 130)

Class V (>130)

#### **Biological data**

White blood cell count G/l (on admission)

Neutrophils (G/l)

Banded forms (G/l)

proBNP ng·L

CRP mg·L

PCT µg·L

Urea mmol·L

Creatinine µmol·L

#### **Microbiological data**

Positive culture

Blood culture, n/N (%)

Urinary culture, n/N (%)

Sputum culture, n/N (%)

Positive urinary antigen

Legionella, n/N (%)

Pneumococcal, n/N (%)

PCR positive for *Mycoplasma pneumoniae*, n/N (%)

PCR positive for *Chlamydia pneumoniae*, n/N (%)

PCR positive for viruses, n/N (%)

PCR positive for SARS-CoV-2, n/N (%)

Endotracheal aspirate, n/N (%)

Bronchoalveolar lavage, n/N (%)

Pleural culture, n/N (%)

#### **Radiological data**

Chest x ray

Patient position

Upright  
Seated  
Supine  
Lateral image, n/N (%)  
Quality  
Inadequate  
Adequate  
Good  
Years of experience of the radiologist  
LDCT  
Quality  
Inadequate  
Adequate  
Good  
Years of experience of the radiologist  
LUS  
Position  
Sitting  
Supine (and lateral)  
Quality  
Inadequate  
Adequate  
Good  
Years of experience of the echographist

At ER discharge  
**Antibiotic prescription, n/N (%)**

Indication  
Pneumonia  
Acute bronchitis  
Exacerbation of COPD  
Urinary tract infection  
Other

At hospital discharge  
Place of discharge  
Rehabilitation  
Home  
LTCF  
ICU  
IMCU

**Quality-of-life at admission\***

---

## 8.2.2 Analysis of the primary outcome

Data analysis should enable the completion of the following table:

Clinician diagnosis	CXR (n=XXX)	LDCT (n=YYY)	LUS (n=ZZZ)
Accuracy, n (%) [95%CI]			
Sensitivity, n/N (%) [95%CI]			
Specificity, n/N (%) [95%CI]			
PPV, n/N (%) [95%CI]			
NPV, n/N (%) [95%CI]			
PLR [95%CI]			
NLR [95%CI]			

With [95%CI] estimated using the Clopper-Pearson method.

### 8.2.2.1 Primary analysis

- The **accuracy of the clinician's diagnosis** will be described by arm using counts and percentages.
- Ninety-five percent confidence interval (95%CI) around **diagnostic accuracy** percentage will be estimated using the Clopper-Pearson method.
- The diagnostic accuracy percentage will be compared between CXR and LDCT using the Cochran-Mantel-Haenszel method stratified on centre. This method allows to estimate:
  - the absolute difference (LDCT - CXR)
  - the standard error of the absolute difference

Under the null hypothesis (imaging examination modality has no effect on diagnostic accuracy), the test statistics (i.e. DR/SE(DR)) follows a standard normal distribution.

We will use the “rr\_rd\_mantel\_haenszel” function of the “risks” package in r:

➤ `rr_rd_mantel_haenszel(data, arm, OUTCOME, center, estimand="rd")`

### 8.2.2.2 Secondary analysis

Similar analysis will be performed to compare the diagnosis accuracy percentage between

- LUS and CXR
- LUS and LDCT

### 8.2.2.3 Analysis of the additional diagnostic performance measures of the clinician

#### Sensitivity and specificity

- Will be described by arm using counts and percentages.
- Ninety-five percent confidence interval (95%CI) will be estimated using the Clopper-Pearson method.
- The Cochran-Mantel-Haenszel method stratified on centre will be used to assess the absolute difference in sensitivity (resp. specificity) between
  - CXR and LDCT
  - CXR and LUS

#### Positive Predictive Value (PPV) and Negative Predictive Value (NPV)

- will be described by arm using counts and percentages.
- Ninety-five percent confidence interval (95%CI) will be estimated using the Clopper-Pearson method.
- Will not be compared between arms

#### Positive Likelihood Ratio (PLR) and Negative Likelihood Ratio (NLR)

- Confidence interval will be estimated by arm using the same asymptotic formula than for risk ratio, since it is a ratio of proportions.
- Will not be compared between arms

### 8.2.2.4 Interrater agreement analysis

For each method (CXR, LDCT, LUS), interrater agreement on the probability of pneumonia – rated on the original three-level Likert scale (low/intermediate/high) – will be assessed between trial physicians and the third (and final) round of reviews by a consensus panel of experts.

Interrater agreement will be evaluated using a weighted kappa score and by calculating the observed percentage of agreement.

The weighted kappa will be estimated using the following “prerecorded” weights:

		Probability of pneumonia at round 3 (panel of experts)		
		Low (excluded or improbable on the 5-point Likert scale)	Intermediate (intermediate on the 5-point Likert scale)	High (likely or confirmed on the 5-point Likert scale)
Probability of pneumonia (Clinician)	Low	1	0.5	0
	Intermediate	0.5	1	0.5
	High	0	0.5	1

A weight of 1 indicates that an observation should count as perfect agreement. A weight of 0.5 means the clinician and the consensus panel of experts are in half agreement (or half disagreement). Finally, they are in complete disagreement when the weight is zero.

#### 8.2.2.5 Sensitivity analysis

In a sensitivity analysis, the **diagnosis of pneumonia will be modified** as follows:

- III. Diagnosis of pneumonia will be considered
  - positive if the probability is rated 'high'
  - negative if the probability is rated 'low' or 'intermediate'

The same analyses as the primary analysis will be performed with this modification of the definition of the diagnosis of pneumonia.

#### 8.2.2.6 Subgroup analysis

The same analyses as the primary analysis will be restrained to the following subgroups:

- Per protocol analysis set
- $\geq 80$  vs.  $<80$  years old
- SARS-CoV-2 infection vs non SARS-CoV-2 infection
- Aspiration pneumonia vs non aspiration pneumonia
- Chronic pulmonary disease vs. no chronic pulmonary disease (Charlson score subscale)
- Patients with obesity (BMI $\geq 30$ )

### 8.2.3 Analysis of the secondary outcomes

For the secondary outcomes that will be compared between arms using a regression model, a single model including all three arms will be used. Effect sizes will be reported for each pairwise comparison:

CXR vs. LDCT

LUS vs. CXR

LUS vs. LDCT

#### 8.2.3.1 Diagnosis by imaging specialists

Diagnostic performance metrics – including overall accuracy, sensitivity, specificity, PPV, and NPV, will be calculated for each imaging specialist across all patients in the full analysis set, regardless of treatment arm. Results will be presented as counts and percentages, with confidence interval estimated using the same method as for the primary analysis.

#### 8.2.3.2 Diagnostic outcomes

Unless otherwise stated, diagnostic outcomes will be analysed solely for descriptive purposes, as count and percentages for qualitative variables, and mean and standard deviation for quantitative variables.

- ❖ **Non-invasive ventilation, pleural puncture, and additional imaging studies ordered** during the acute setting will be described as follow

Diagnostic outcomes	CXR (n=XXX)	LDCT (n=YYY)	LUS (n=ZZZ)
Patients with additional studies ordered, n (%)			
Yes (nb_imaging_ordered>0)			
No			
Number of additional studies ordered, mean (sd)			
Overall number (nb_imaging_ordered)			
Number of chest X Ray			
Number of Pulmonary CT scanner			
Number of Lung US			
Number of Echocardiography			
Patients with non-invasive ventilation, n (%)			
Patients with pleural puncture, n (%)			

The proportion of patients with additional studies ordered will be compared between arms using a linear probability model (binomial model with link Identity)

- ❖ The **following outcomes** will be described in **patients with a 'low' probability of pneumonia** according to the study expert:
  - Alternative diagnosis according to the study expert
- ❖ The **following outcomes** will be described in **patients with a 'intermediate' or 'high' probability of pneumonia** according to the study expert:
  - Probability of aspiration pneumonia according to the study expert
  - Type of pneumonia (viral & aspiration) according to the study expert

Diagnostic outcomes in patients with 'low' probability of pneumonia according to the study expert	CXR (n=XXX)	LDCT (n=YYY)	LUS (n=ZZZ)
Alternative diagnosis according to the study expert, n (%)			
Cardiac Failure			
Exacerbation COPD/emphysema/asthma			
Acute bronchitis			
Pulmonary malignancy			
Interstitial lung disease			
Pneumothorax			
Other			
Probability of aspiration pneumonia according to the study expert, n (%)			
Low			
Intermediate			
High			
Type of pneumonia according to the study expert, n (%)			
Viral			
Bacterial			

- ❖ **Concomitant diagnosis according to the study expert** will be described in **patients with an 'intermediate' or 'high' probability of pneumonia** according to the study expert:

Diagnostic outcomes in patients with 'intermediate' or 'high' probability of pneumonia according to study expert	CXR (n=XXX)	LDCT (n=YYY)	LUS (n=ZZZ)
Concomitant diagnosis according to the study expert, n (%)			
Cardiac Failure			
Exacerbation COPD/emphysema/asthma			
Acute bronchitis			
Pulmonary malignancy			
Interstitial lung disease			
Pneumothorax			
Other			

- ❖ **Unmasked imaging modalities in emergency (CXR, LDCT, LUS)** will be described overall as count and frequency (one overall description).

#### 8.2.3.3 Treatment outcome

Number of antibiotic free days at day 30 will be compared between the three arms using a linear regression model adjusted on centre with a bootstrap method for 95%CI. P values will be computed by inverting the corresponding confidence interval (Thulin 2024: modern statistics with R).

- a subgroup analysis excluding exacerbation of COPD, where the need for antibiotic therapy is still debated, will be performed.

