### 3.5 Sample size, null and alternative hypothesis

**The final recruitment objective was 165 patients in each arm, for a total of 495 patients.**

The sample size calculation was based on the following hypotheses: based on the PneumO-LD-CT cohort, the expected accuracy of the clinician's diagnosis is 68% when based on CXR and 84% when based on LDCT. With an expected improvement of 16% of the accuracy using LDCT instead of CXR, 150 patients will be required in each arm to demonstrate the superiority of LDCT over CXR with a two-sided alpha error of 0.05 and a power of 90%. Allowing for a 10% drop-out after randomisation, the final recruitment objective is 165 patients in each arm, for a total of 495 patients.

**Null hypothesis:** the proportion of accurate clinician's diagnosis is the same on CXR and LDCT.

**Alternative hypothesis:** the proportion of accurate clinician's diagnosis is different between CXR and LDCT.

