#### 8.2.3.4 Clinical outcomes

- **All-cause mortality at 30 days** will be
  - estimated by arm using the Kaplan-Meier method
  - compared between arms through pairwise comparisons using a log-rank test stratified by centre (three pairwise tests will be performed)
  - and the complementary log-log transformation will be applied to calculate the 95% confidence intervals for the 30-day survival estimates
- **All-cause mortality at 30 days** will be described only
- **In-hospital mortality**
  - will be described by arm as count and percentages
  - will be compared between arms using a logistic regression model adjusted on centre. Odds ratio will be reported with 95% confidence intervals
- Number of patients hospitalised after emergency and number of patients discharged after emergency will be described by arm as count and percentages
- **Length of hospital stay**
  - Will be analysed **among all randomized patients, and repeated among hospitalized patients only** (excluding those discharged after emergency department presentation)
  - Will be compared between arms using a linear regression model adjusted on centre with a bootstrap method for 95%CI.
  - Pvalues will be computed by inverting the corresponding confidence interval (Thulin 2024: modern statistics with R).
- **Unplanned transfer to the ICU/IMCU within 30 days after initial admission/evaluation**
  - Will be analysed **among all randomized patients, and repeated among hospitalized patients only** (excluding those discharged after emergency department presentation)
  - Will be described by arm as count and percentages
  - Will be compared between arms using a logistic regression model adjusted on centre. Odds ratio will be reported with 95% confidence intervals.
- The following outcomes will be described by arm as count and percentages **in patients discharge alive**. Those outcomes will not be compared between arms:
  - **Admission to rehabilitation through 3 months in patients discharge alive**
  - **Transfer to LTCF through 3 months in patients discharge alive**
  - **All-cause readmission to acute care setting in patients discharge alive**
  -
- The **quality of life 30 days and 90 days** will be described by arm as median and IQR **in patients discharge alive**. Quality of life will not be compared between arms

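### Antibiotic-free days and length of stay are adjusted for centre alone, which gives up some precision; the repeat analysis excluding COPD exacerbation names no variable, and every candidate arises after imaging.

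*SAP*

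**What the plan says.** For the only treatment outcome, SAP 8.2.3.3 says: "Number of antibiotic free days at day 30 will be compared between the three arms using a linear regression model adjusted on centre", with bootstrap confidence intervals. For length of stay, SAP 8.2.3.4 says: "Will be compared between arms using a linear regression model adjusted on centre with a bootstrap method for 95%CI". Neither model names a baseline prognostic covariate. Centre is the only stratification factor (SAP 3.2).

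SAP 8.2.3.3 then adds: "a subgroup analysis excluding exacerbation of COPD, where the need for antibiotic therapy is still debated, will be performed". It gives no variable, rater or time point. Protocol 5.1, secondary analysis 6, has the same exclusion, equally undefined. There it is called a sensitivity analysis and is attached to a competing-risk analysis that the SAP has since replaced.

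The data that could be used are already collected. The SAP 3.4 timeline puts demographics, medical history, vital signs and laboratory tests at screening, before randomisation. SAP Table 1 lists CURB-65, CRP and, as a comorbidity, COPD. SAP 8.4 prescribes complete-case analysis.

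**The concern.** There are two separate issues.

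**Precision.** The trial was sized on diagnostic accuracy. No standard deviation, target difference or power is stated for antibiotic-free days or length of stay. Antibiotic use carries the stewardship argument in the protocol's rationale, so avoidable noise in that comparison matters. Age, severity and CRP plausibly predict both outcomes and can be taken from values recorded before allocation.

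**The COPD exclusion.** Removing patients from a randomised comparison is safe when the reason is fixed before allocation. If the reason is a label assigned after the image has been read, or with the outcome in view, the retained groups may no longer be comparable. The repeat analysis then cannot show clearly whether the main result is robust to COPD exacerbations.

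**Working it through.** **The plan's own figure.** SAP 3.5 assumes that the accuracy of the clinician's "diagnosis is 68% when based on CXR and 84% when based on LDCT", with a "two-sided alpha error of 0.05 and a power of 90" per cent. With pooled proportion 0.76:

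n = [1.960 × √(2 × 0.76 × 0.24) + 1.282 × √(0.68 × 0.32 + 0.84 × 0.16)]² / 0.16² = 148 per arm.

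The SAP states 150, at which power is 90.4%. The target of 165 is 150 × 1.10. The figure reproduces, but it concerns accuracy and says nothing about the two outcomes here.

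**Precision.** Let R² be the share of outcome variance explained by the added covariates beyond centre. The standard error is multiplied by √(1 − R²), and the gain is equivalent to multiplying the sample size by 1/(1 − R²). At 150 per arm and two-sided 0.05, the difference detectable with 80% power is √(1 − R²) × (1.960 + 0.842) × √(2/150) standard deviations. R² is assumed throughout.

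| R² | SE factor | Equivalent sample size | Detectable difference (SD) | Power for 0.30 SD |
|---|---|---|---|---|
| 0 | 1.000 | 1.00 | 0.323 | 73.8% |
| 0.05 | 0.975 | 1.05 | 0.315 | 76.0% |
| 0.10 | 0.949 | 1.11 | 0.307 | 78.2% |
| 0.15 | 0.922 | 1.18 | 0.298 | 80.5% |
| 0.20 | 0.894 | 1.25 | 0.289 | 82.8% |

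**Possible sources of the COPD label.**

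| Source | When and by whom | Difficulty |
|---|---|---|
| "Exacerbation of COPD" as antibiotic indication (SAP Table 1, at ER discharge) | After the allocated image; clinician knows the arm | Can depend on arm. Listed under antibiotic prescription, so on the natural reading only treated patients carry it |
| Clinician's principal alternative diagnosis (Protocol 4.3) | Before ED discharge, after the allocated image; same clinician | Can depend on arm. Protocol 4.3 discourages antibiotics for pneumonia after a low rating but allows them under another documented diagnosis, with COPD exacerbation as an example |
| Expert alternative or concomitant diagnosis, Delphi round 1 (SAP 8.1.2.2) | Retrospective; blinded to arm, with results of all three modalities | Round 1 material includes antibiotic treatment and length of stay (expert panel method, part 2). The category also covers emphysema and asthma |

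No source precedes randomisation. COPD history does not share the problem, because allocation cannot change it.

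**Does the exclusion have a predictable effect?** Two illustrations, with every input assumed and no true arm effect:

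- Five per cent of the LDCT arm are labelled as exacerbation and dropped. They have 23 antibiotic-free days each, and the arm mean is 25.2. The retained mean is (25.2 − 0.05 × 23)/0.95 = 25.32, a shift of about +0.1 day.
- Take 50% pneumonia, 15% COPD exacerbation and 35% other, with 8, 6 and 3 antibiotic days. In the CXR arm the label is given to 2%, 60% and 5% of these groups. The retained mean is (0.49 × 22 + 0.06 × 24 + 0.3325 × 27)/0.8825 = 24.02. If LDCT raises the last two rates to 90% and 15%, its retained mean is (0.49 × 22 + 0.015 × 24 + 0.2975 × 27)/0.8025 = 23.89, a difference of −0.13 day. If it lowers them to 40% and 2%, the difference is +0.03 day.

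The sign depends on whether the dropped patients use more or less antibiotic than those retained.

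**The case against.** The centre-only model is not an error. It respects the stratification, matches the protocol's site-adjusted comparisons, and is unbiased under randomisation. All of that stands. A reader might infer that the unadjusted comparison is biased; the documents do not support this, and the only loss is precision, of undocumented size.

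The timing evidence also has limits. Severity scores have no time point of their own. The baseline list in SAP 6.3 includes radiological data and treatment, which come later. Protocol Table 1 puts demographics and medical history in the same column as randomisation. CRP is only one of several alternative infection criteria, so it may be missing for some patients. It is therefore too strong to say that everything is documented as collected before allocation. CURB-65 should be built from screening values.

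On COPD, a reader might infer that the SAP states an exclusion on a post-image diagnosis. It does not: it leaves the variable undefined, and the post-image source is an inference from the items available. A reader might also suppose that LDCT turns pneumonia into exacerbation whichever label is used. That route applies only to the clinician's labels. The experts are blinded to arm and have the results of all three modalities; the difficulty there is sight of antibiotic treatment. The earlier cohort's figures (30% downgraded, 15% upgraded; Protocol 2) describe changes in the probability of pneumonia, not relabelling as COPD.

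Finally, the shifts above are small. If the standard deviation were 4 to 8 days (assumed), 0.323 SD would be 1.3 to 2.6 days, against about 0.1 day. That stands as a reason not to claim a material bias. It does not settle which patients are to be excluded.

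**Conclusion.** Both parts hold in modest form, and neither touches the primary outcome.

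The centre-only models are valid but less precise than they could be. Standard errors would be about 2.5 to 8% smaller if the covariates explain 5 to 15% of the variance, which is an assumption.

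The COPD exclusion is undefined, and every available definition is post-randomisation. It can depend on the arm through a clinician label, or on the outcome through an expert label. The size and direction of any bias cannot be derived from the documents, so the finding is that the analysis is hard to interpret, not that it is shown to be wrong. Nor does it follow that the exclusion should be replaced by one on COPD history. The stated reason is doubt about antibiotics in exacerbations, and a history-based exclusion would also remove COPD patients who have pneumonia.

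**What to change.** **Models (SAP 8.2.3.3 and 8.2.3.4).** Before unblinding, pre-specify age, CURB-65 and log CRP, from screening values, as covariates alongside arm and centre in both linear models. Fill missing baseline values with the overall mean, as a stated exception to SAP 8.4, so that no patient is lost. Keep the centre-only model as supportive.

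**COPD (SAP 8.2.3.3).** Add a report of the arm effect on antibiotic-free days by baseline COPD history, with an arm-by-history interaction, as the protected comparison. Keep the exclusion on exacerbation as exploratory only, name its source variable, rater and time point, and report the number excluded by arm.

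**Cost.** A few lines of text and code, and no new data. The SAP was finalised after enrolment but before analysis, so the change can still be pre-specified if unblinding has not occurred; it should be listed in SAP 9 as a departure from the protocol's site-only adjustment. The COPD-history analysis answers a slightly different question, because it groups COPD patients with pneumonia together with those in exacerbation. It is also imprecise. With a share q of patients having COPD, and equal variances, the interaction's standard error is √(1/[q(1 − q)]) times that of the overall arm difference. That is at least twice as large, since q(1 − q) cannot exceed 0.25. It should be reported as an estimate with its interval, not as a test expected to be decisive.
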